Nothing herein is to be disclosed in any way without the prior
express written permission of W. L. Gore & Associates, Inc.

**Evaluation of the GORE® TAG® Thoracic Branch Endoprosthesis (TBE Device) in the
Treatment of Lesions of the Aortic Arch and Descending Thoracic Aorta**

Protocol Number: SSB 11-02

W. L. Gore & Associates, Inc.
Medical Products Division

23Nov 2020

NCT # 02777528

PROTOCOL SUMMARY

Subjects enrolled on the SSB 11-02 Protocol prior to a site's IRB approval of Revision 4 should be followed under Revision 3 of the Protocol located in Appendix E (US only).

Study Summary

Study Title	Evaluation of the GORE® TAG® Thoracic Branch Endoprosthesis (TBE Device) in the Treatment of Lesions of the Aortic Arch and Descending Thoracic Aorta
Protocol Number	SSB 11-02
Revision	10
IDE or PMA Number	G130120
Sponsor	W. L. Gore & Associates, Inc. [REDACTED]
Sponsor (Japan)	W. L. Gore & Associates G.K. Medical Products Division [REDACTED]
Study Design	Prospective, non-randomized, multicenter study with four independent arms consisting of a total of seven cohorts: 
 • Zone 2 – Aneurysm, hypothesis-driven analysis • Zone 2 – Non-aneurysm aortic lesions which are anatomically suitable for treatment with the TBE Device, descriptive analysis 
 ○ Dissection cohort ○ Traumatic Transection cohort ○ Other isolated lesion types • Zone 0/1 – Aneurysm, hypothesis-driven analysis • Zone 0/1 – Non-aneurysm aortic lesions which are anatomically suitable for treatment with the TBE Device, descriptive analysis 
 ○ Dissection cohort ○ Other isolated lesion types
Study Objective	Determine whether the GORE® TAG® Thoracic Branch Endoprosthesis is safe and effective in treating lesions of the aortic arch and descending thoracic aorta
Study Endpoint(s)	Primary Endpoint- Zone 2 Subjects (Aneurysm Cohort) Composite of the following events from the time of enrollment through one year: 
 • Device Technical Success • Absence of the following: 
 ○ Aortic rupture; ○ Lesion-related mortality;

	
 ○ Disabling stroke; ○ Permanent paraplegia; ○ Permanent paraparesis; ○ New onset renal failure requiring permanent dialysis; ○ Additional unanticipated post-procedural surgical or interventional procedure related to the device, procedure, or withdrawal of the delivery system. 
Primary Endpoint- Zone 0/1 Subjects (Aneurysm Cohort) Composite of the following events from time of enrollment through one month following endovascular procedure:
 
 ● Initiation of the index endovascular procedure following the debranching procedure ● Device Technical Success for the index endovascular procedure ● Absence of the following: 
 ○ Aortic rupture; ○ Lesion-related mortality; ○ Disabling stroke; ○ Permanent paraplegia; ○ Permanent paraparesis; ○ New onset renal failure requiring permanent dialysis; ○ Additional unanticipated post-procedural surgical or interventional procedure related to the device, procedure, or withdrawal of the delivery system.
Subject Population	Subjects with thoracic aortic lesions which require coverage of the left subclavian artery, left common carotid artery and/or the brachiocephalic trunk/innominate artery for effective treatment.
Number of Subjects	
Total Enrollment of 175-465 Subjects across four independent arms with a total of seven cohorts as follows:
 
 ● Zone 2 – Aortic Aneurysm; A maximum of 115 Subjects 
 ○ Primary Enrollment (n=85 Subjects) ○ Continued Access Enrollment (maximum 30 Subjects) ● Zone 2 – Non-aneurysm aortic lesions; A maximum of 200 Subjects in all cohorts combined. 
 ○ Dissection cohort (minimum 20 Subjects) ○ Traumatic Transection cohort (minimum 10 Subjects) ○ Other isolated lesion types

	
 • Zone 0/1 – Aortic Aneurysm; 50 Subjects • Zone 0/1 – Non-aneurysm aortic lesions; A maximum of 100 Subjects in all cohorts combined. 
 ○ Dissection cohort (minimum 10 Subjects) ○ Other isolated lesion types
Number of Sites	Up to 40 sites in the U.S. (Zone 2 and Zone 0/1) and up to 5 sites in Japan (Zone 0/1).
Coordination PI	

Expected Time to Complete Enrollment	
 • Zone 2 - Aortic Aneurysm Subject accrual: 18-24 months • Zone 0/1 - Aortic Aneurysm Subject accrual: 48-60 months • Follow-up – Five years from treatment date Total study duration –Ten years
Schedule of Events Zone 2 Cohorts	
Screening Evaluation: (Within 30 days prior to enrollment unless otherwise noted)
 
 • Physical examination, medical history • Modified Rankin Scale • Spinal Cord Ischemia Scale • NIH Stroke Scale • Spiral Computed Tomographic Angiography (CTA) of the chest, abdomen, and pelvis (contrast only) within 90 days prior to enrollment • Serum creatinine concentration 
Procedure:
 
 • Endovascular repair with the TBE Device with distal extension using the Conformable GORE® TAG® Thoracic Endoprosthesis as needed • Post deployment angiogram

	
Post Procedure: (Performed prior to discharge unless otherwise noted)
 
 • Physical examination • Modified Rankin Scale • Spinal Cord Ischemia Scale • NIH Stroke Scale • In addition, NIH Stroke Scale should be performed for any Subject suspected of having a stroke event that undergoes the treating site's stroke Protocol during the study interval from the initiation of index endovascular procedure until discharge, and should be performed as soon as possible after learning of the event 
Follow-Up Evaluations: Intervals: 1, 6, 12, 24, 36, 48, and 60 months post-treatment
 
 • Physical examination • Modified Rankin Scale (also completed at 3 months for Subjects suspected of experiencing a stroke event through 30 days) • Spinal Cord Ischemia Scale • Spiral CTA of the chest (contrast) • NIH Stroke Scale (one month only) • Dissection Subjects only: Spiral CTA of the chest, abdomen, and pelvis (contrast) • Spiral CT of the chest (non-contrast - one month only, or if endoleak suspected) • Dissection Subjects only: Spiral CTA of the chest, abdomen, and pelvis (non-contrast - one month only, or if endoleak suspected)

Schedule of Events Zone 0/1 Cohorts
	
Screening Evaluation: (Within 30 days prior to enrollment unless otherwise noted)
 
 • Physical examination, medical history • Modified Rankin Scale • Spinal Cord Ischemia Scale • NIH Stroke Scale • Serum creatinine concentration • Spiral Computed Tomographic Angiography (CTA) of the chest, abdomen, and pelvis (contrast only) within 90 days prior to the Phase 2 procedure • Radiological Evaluation of the Head/Neck within 90 days prior to Phase 1 procedure 
Phase 1 Evaluation at least 24 hours but no more than 60 days following the completion of the revascularization procedure:
 
 • Physical examination • Modified Rankin Scale

- Spinal Cord Ischemia Scale
- In addition, NIH Stroke Scale should be performed for any Subject suspected of having a stroke event that undergoes the treating site's stroke Protocol during the study interval from the initiation of surgical revascularization procedure until discharge post-index endovascular procedure, and it should be performed as soon as possible after learning of the event

Phase 2 Procedure at least 24 hours but no more than 60 days following the completion of the revascularization procedure:

- Endovascular repair with the TBE Device
- Post deployment angiogram

Post Procedure:

(Performed prior to discharge unless otherwise noted)

- Physical examination
- Modified Rankin Scale
- Spinal Cord Ischemia Scale
- NIH Stroke Scale
- In addition, NIH Stroke Scale should be performed for any Subject suspected of having a stroke event that undergoes the treating site's stroke Protocol during the study interval from the initiation of surgical revascularization procedure until discharge post-index endovascular procedure, and it should be performed as soon as possible after learning of the event

Follow-Up Evaluations:

Intervals: 1, 6, 12, 24, 36, 48, and 60 months post-treatment

- Physical examination
- Modified Rankin Scale (also completed at 3 months for Subjects suspected of experiencing a stroke event through 30 days)
- Spinal Cord Ischemia Scale
- NIH Stroke Scale (one month only)
- Spiral CTA of the chest (contrast)
- Dissection Subjects only: Spiral CTA of the chest, abdomen and pelvis (contrast)
- Spiral CT of the chest (non-contrast – one month only, or if endoleak suspected)
- Dissection Subjects only: Spiral CTA of the chest, abdomen and pelvis (non-contrast – one month only, or if endoleak suspected)

Additional Information

[REDACTED]

[REDACTED]

1.0 Introduction

This Statistical Analysis Plan (SAP) describes the statistical analyses planned to address the objectives of the evaluation of the GORE[®] TAG[®] Thoracic Branch Endoprosthesis (TBE Device) in the treatment of lesions of the aortic arch and descending thoracic aorta.

2.0 Study Design Overview

This section consists of relevant elements from the study protocol, including (as applicable):

2.1 Objectives

2.1.1 Primary Objective(s)

The primary objective of the study is to determine whether the GORE[®] TAG[®] Thoracic Branch Endoprosthesis (TBE device) is safe and effective in treating thoracic aortic pathologies. Specifically, the objective will be to perform hypothesis-driven analysis of the device's safety and effectiveness in the treatment of aortic aneurysms requiring proximal device placement in Zone 0/1 & Zone 2 of the thoracic aorta, respectively. Due to the potential applicability of the TBE Device in additional pathologic presentations, enrollment of anatomically suitable non-aneurysm patients will also be allowed to provide additional clinical data to characterize performance in these applications.

2.2 Design Summary

This will be a non-randomized, multicenter, prospective study conducted at up to forty-five (45) Clinical Investigative Sites (referred to as "Sites" in the remainder of this document), with up to 40 sites in the U.S and up to 5 sites in Japan with the objective of determining whether the TBE device is safe and effective in treating lesions of the aortic arch and descending thoracic aorta. A minimum of 175 and up to a total of 465 Subjects will be enrolled across four independent study arms consisting of seven cohorts as described below. The anatomically suitable non-aneurysm cohorts will be referred to as the Non-Aneurysm Lesion (NAL) Cohorts.

The study will consist of seven cohorts described as follows:

- Zone 2, aneurysm patients (N=115, maximum)
 - Zone 2, aneurysm patients, Primary Enrollment (N=85)
 - Zone 2, aneurysm patients, Continued Access Enrollment (N=30, maximum)
- Zone 2, anatomically suitable non-aneurysm patients, descriptive analysis (N=200, maximum)
 - Dissection cohort (N=20 minimum)
 - Traumatic Transection cohort (N=10 minimum)
 - Other isolated lesion types cohort (No minimum)
- Zone 0/1, aneurysm patients, hypothesis driven (N=50, 0-10 Subjects from Japan) NOTE: due to removal of the 49/53mm device sizes from this trial, any Subjects enrolled with these device sizes will not be counted as part of this N=50 enrollment and replacement Subjects will be enrolled to keep N=50)
- Zone 0/1, anatomically suitable non-aneurysm patients, descriptive analysis (N=100, maximum)

CONFIDENTIAL INFORMATION

- Dissection cohort (N=10 minimum)
- Other isolated lesion types cohort (No minimum)

The Zone 2 aneurysm cohort will consist of 85 subjects accrued during the Primary Enrollment period along with a maximum of 30 subjects accrued during the Continued Access Enrollment period. Any Zone 2 training cases enrolled from Japan would not be included in PMA analysis, nor do they count towards enrollment minimums/maximums as shown above. However, once enrolled, the Japan Zone 2 training cases may be included for some analysis.

The maximum number of Subjects that may be enrolled at a single site is as follows:

- Zone 2, aneurysm patients, 17 Subjects
- Zone 0/1, aneurysm patients, 8 Subjects in US, 4 Subjects in Japan
- Zone 2 and Zone 0/1, anatomically suitable non-aneurysm patients, all cohorts, will not have a maximum per site as they are for descriptive analysis only

See Figure 1 of a schematic representation of this study design.

[figure not shown]

Figure 1. Study Design Schematic

*Japan may contribute to the Zone 0/1 cohort. They will also conduct two training cases in Zone 2 Subjects which will not be included in the min and max for Zone 2 enrollment.

2.3 Study Outcomes

All outcomes (in addition to being described in two below subsections) are displayed in **Appendix A**. This table from the study protocol describes the responsible party for the determination and adjudication of each specific Primary Endpoint **Describes the responsible party** in addition, there was a

third column added for this SAP to describe what Case Report Form (CRF) and question the study outcome will be determined from.

2.3.1 Primary Endpoint

The Primary Endpoints for the two hypothesis-driven study cohorts are described below. Definitions for these events are provided in the study protocol.

2.3.1.1 Zone 2 Aneurysm Cohort

The Primary Endpoint for the Zone 2 aneurysm cohort will be a composite of the following events through 12 months (through day 546 unless otherwise specified in study protocol component definitions) following the index endovascular procedure:

- Device Technical Success
- Absence of the following:
 - Aortic rupture;
 - Lesion-related mortality;
 - Disabling stroke
 - Permanent paraplegia
 - Permanent paraparesis
 - New onset renal failure requiring permanent dialysis
 - Additional unanticipated post-procedural surgical or interventional procedure related to the device, procedure, or withdrawal of the delivery system.
- 2.3.1.2 Zone 0/1 Aneurysm Cohort

[figure not shown]
The Primary Endpoint for the Zone 0/1 aneurysm cohort will be Strategy Success.

Strategy Success (For planned staged procedures – landing zone optimization, transposition, and device placement – through one month following last planned procedure) and is defined as follows: a composite of the following events from the time of enrollment through one month following the index endovascular procedure (through day 59 unless otherwise specified in study protocol component definitions):

[figure not shown]
- Initiation of the index endovascular procedure following the debranching procedure
- Device technical success for the index endovascular procedure
- Absence of the following :
 - Aortic rupture
 - Lesion-related mortality
 - o Disabling Stroke
 - Permanent paraplegia
 - Permanent paraparesis
 - New onset renal failure requiring permanent dialysis

GORE CONFIDENTIAL INFORMATION

 Additional unanticipated post-procedural surgical or interventional procedure related to the device, procedure, or withdrawal of the delivery system.

GORE CONFIDENTIAL INFORMATION

2.4 **Statistical Hypotheses**

- 2.4.1 Performance Goal Derivation
 - 2.4.1.1 Zone 2 Aneurysm Cohort

Historical TAG/CTAG results (TAG 99-01, TAG 03-03, TAG 04-02, TAG 05-02, TAG 08-03) were re-analyzed to determine the Zone 2 aneurysm cohort performance goal for the Primary Endpoint (see study protocol for this data). Subjects treated for DTA aneurysms with proximal device placement in Zone 2

GORE CONFIDENTIAL INFORMATION

were identified in the historical TAG/CTAG studies. Using the data to the extent possible from historical TAG/CTAG Zone 2 aneurysm studies, the primary event rate through 12 months was calculated for these Subjects applying the Primary Endpoint definitions planned for the prospective Zone 2 aneurysm cohort. Subjects with one or more Primary Endpoint events through the 12 month window (i.e. through study day 546) were counted as failures (those with >1 event counted just once as failures). Subjects without an event through 12 months had to have imaging done within the 12 month time window in order to count as successes. The percentage of TAG/CTAG Subjects successful for the Primary Endpoint through 1 Year was 81%. The lower bound of the 95% confidence interval on this result is 71% (based on a combined sample size of 75 Subjects as displayed in the study protocol). However, this result did not include performance on device technical success (including patency and unanticipated additional procedure) at procedure (this was estimated to be 5-7%). Based on these results and the potential for these additional endpoint events, the performance goal was set at 64%.

2.4.1.2 Zone 0/1 Aneurysm Cohort

A systematic literature review of hybrid repair literature was conducted (see study protocol for in-depth description of this literature review). Key results that were consistently identifiable from the review included perioperative death, neurological events and spinal cord ischemia, all of which are part of the Zone 0/1 Primary Endpoint. The results were individually summarized (i.e., a rate for each outcome was calculated across the identified literature) and then summed up; the estimated total percent of these events was 23.6%. Additional events included in the Primary Endpoint of the Zone 0/1 statistical arm are renal failure and the components of technical success. To account for these additional factors, an adjustment of 11% to the overall point estimate from the literature analysis was employed, increasing the anticipated point estimate from historical results to 34.6%. To account for potential variability in the new study population an additional margin of 5% was incorporated. This additional adjustment to the performance goal is justified given the potential for underreporting of key events in literature and national databases. Due to this consideration, the study performance goal (success) for the proposed Zone 0/1 Primary Endpoint was set at 60%.

2.4.2 Zone 2 Aneurysm Cohort Hypothesis

The analysis of the Primary Endpoint for this cohort is intended to test the hypothesis that the success exceeds the performance goal of 64%. Using the performance goal of 64% with Primary Endpoint success through 12 months, the following hypothesis will be tested:

[figure not shown]
> $H_0: P_{s2} \le 0.64$ H_{A} : $P_{s2} > 0.64$

GORE CONFIDENTIAL INFORMATION

2.4.3 Zone 0/1 Aneurysm Cohort Hypothesis

The analysis of the Primary Endpoint for this cohort is intended to test the hypothesis that the success exceeds the performance goal of 60%. Using the performance goal of 60% with Primary Endpoint success through one month, the following hypothesis will be tested:

To meet the performance goal

of 60%, a point estimate of > 74% Primary Endpoint success for 50 patients through one month is required. No attrition was accounted for.

Sample size calculations were determined using PASS 13 one-sided exact test for one proportion.

3.0 Study Treatment Arms

3.1 Test Arm

There are 4 arms (2 hypothesis-driven test arms) and seven study cohorts, described again as follows:

- Zone 2, aneurysm patients (N=115, maximum)
 - Zone 2, aneurysm patients, Primary Enrollment (N=85)
 - Zone 2, aneurysm patients, Continued Access Enrollment (N=30, maximum)
- Zone 2, anatomically suitable non-aneurysm patients, descriptive analysis (N=200, maximum)
 - Dissection cohort (N=20 minimum)
 - Traumatic Transection cohort (N=10 minimum)
 - Other isolated lesion types cohort (No minimum)
- Zone 0/1, aneurysm patients, hypothesis driven (N=50, 0-10 Subjects from Japan) NOTE: due to removal of the 49/53mm device sizes from this trial, any Subjects enrolled with these device sizes will not be counted as part of this N=50 enrollment and replacement Subjects will be enrolled to keep N=50.)
- Zone 0/1, anatomically suitable non-aneurysm patients, descriptive analysis (N=100, maximum)
 - Dissection cohort (N=10 minimum)
 - Other isolated lesion types cohort (No minimum).

A variety of pathologies can affect the thoracic aorta. These include aneurysms, dissections (including variants of dissection) and traumatic pathologies including transection. Aneurysm and dissection may affect any area of the thoracic aorta, including the ascending, arch or descending, whereas traumatic transections are typically located in the descending thoracic aorta (DTA). The study protocol has more detail about each of these pathologies and all lesion inclusion/exclusion criteria that are needed for possible study enrollment. However, at a minimum, the following are pathology inclusion criteria for the study cohorts (all must be a thoracic aortic pathology deemed to warrant surgical repair which requires proximal graft placement in Zone 0-2):

[figure not shown]
- a) Aneurysms:
 - i) Fusiform aneurysm (≥55 mm), or
 - ii) Fusiform aneurysm (>2 times native aortic diameter), or
 - iii) Saccular aneurysm (no diameter criteria)
- b) Non-aneurysms
 - i) Intramural hematoma (no diameter criteria), or
 - ii) Penetrating aortic ulcer (no diameter criteria), or
 - iii) Traumatic aortic transection (no diameter criteria), or
 - iv) Other isolated lesion with non-diseased proximal and distal landing zone, or

- v) Type B aortic dissection requiring treatment for rupture or impending rupture, malperfusion syndrome, rapid expansion, uncontrollable pain, aneurysmal dilatation or prophylactic reasons, or
- vi) Residual aortic dissection following surgical repair of Type A aortic dissection requiring treatment.

See **Figure 2** for a visual overview of the required placement of the proximal extent of the TBE device (to see the difference between Zone 0/1 and Zone 2 cases).

Figure 2. Anatomical Landing Zone Map for Thoracic Endovascular Stent Graft Placement¹

4.0 Study Data Collection

This section contains information on data collected. Subject enrollment definition, withdrawal, and lost-to-follow-up details are explained in the study protocol.

4.1 Data Collected

Data will be collected in Case Report Forms (CRFs) and include the following:

- Cohort Enrollment Status
- Demographics
- Eligibility (Inclusion/Exclusion) Criteria
- Medical History
- Case Planning (form for each Zone and separately by Zone for dissection cases)
- Subject Physical Evaluations and Pressures
- Modified Rankin and Spinal Cord Ischemia Assessments
- Risk Assessments
- Trauma (Glasgow Coma and ISS) Assessments for Traumatic Transection Cases
- NIH Stroke Scale
- Pre-Imaging Site Assessment
- Pre-Imaging Corelab Assessment (separate forms for Aneurysm/Isolated Lesion and Dissection)

CONFIDENTIAL INFORMATION

- Interval (Post) Imaging Assessments (Site, Corelab Aneurysm/Isolated Lesion, Corelab Dissection, Corelab Overall Device Events)
- Device Accountability (Pre and Post) •
- Device Deficiencies
- **Revascularization Procedure**
- Initial Endovascular Procedure
- Missed Visits
- Adverse Events (AEs) and Treatments
- Safety Narratives
- CEC Adjudication
- Medications of Interest
- Study Completion/Discontinuation

4.2 **Study Data Collection Intervals**

Table 1 and Table 2 outline the required procedures at each follow-up visit for the respective study cohorts by Zone.

	Screening	Treatment	Discharge	1 month	6 months	12 months	24, 36, 48, and 60 months
Informed Consent	Х						
Demographics and Medical History	х						
Physical examination	Х		Х	х	х	х	Х
Modified Rankin Scale ^a	Х		х	Xp	х	х	Х
Spinal Cord Ischemia Scale ^a	х		х	х	х	х	х
Brachial and Ankle Pressures (Optional)	х		X c	х	х	х	x
Serum Creatinine Concentration	Х						
Spiral CTA (contrast) ^d	Xe			х	х	x	X
Spiral CT (non-contrast) ^d				Х			
Angiogram at Completion of Procedure		х					
NYHA Score, ASA Score	х						
ISS Score, Glasgow Coma Score (Traumatic Transection Subjects only)	x						
NIH Stroke Scale (NIHSS) ^f	х		х	х			

Table 1: Zone 2 Subject Evaluations and Post-Treatment Follow-up Schedule

^a If subject is unable to return to the site for a follow-up visit, they may be contacted by telephone to evaluate the Modified Rankin Scale and Spinal Cord Ischemia Scale

^b For subjects suspected of having a stroke event within 30 days following the index endovascular procedure an additional MRS score should be completed at 90 days following the suspected stroke event but no greater than 120 days post index endovascular procedure.

^cWithin 48 hours of index endovascular procedure

^d CTA of chest/abdomen/pelvis at Screening. CTA of chest at all follow-up visits, except for Dissection Subjects who must have a CTA of chest/abdomen/pelvis at all visits. Imaging Guidelines for CT are located in Protocol. MRA may be used in place of CTA during follow-up if the Subject is contraindicated for CTA.

^e Screening CTA must be ≤ 90 days prior to enrollment

^f NIH Stroke Scale should be performed for all subjects during Screening, Discharge and 1 Month visits. NIHSS should also be performed for any Subject suspected of having a stroke event that undergoes the treating site's stroke Protocol during the study interval from the initiation of the index endovascular procedure until discharge. The scale should be performed as soon as possible after learning of the suspected event.

		Tr	reatm	ent					24
	Screening	Phase 1 Procedure	Phase 1 Evaluation	Phase 2 Procedure	Discharge	1 month	6 months	12 months	24, 36, 48, and 60 months
Informed Consent	х								
Demographics and Medical History	х								
Physical Examination	х		X۵		х	х	х	х	х
Modified Rankin Scale ^c	х		x		х	Xď	х	x	х
Spinal Cord Ischemia Scale ^c	х		x		х	х	х	x	х
Brachial and Ankle Pressures (Optional)	х		x		X e	х	х	х	х
Serum Creatinine Concentration	х								
Spiral CTA (contrast) ^f	Xg					х	х	x	х
Spiral CT (non-contrast) ^f						х			
Angiogram at Completion of Procedure				x					
CTA of the Head/Neck h	х								
NYHA Score, ASA Score	х								
ISS Score, Glasgow Coma Score (Traumatic Transection Subjects only)	x								
NIH Stroke Scale (NIHSS) ⁱ	х				x	x			

Table 2: Zone 0/1 Subject Evaluations and Post-Treatment Follow-up Schedule

^a Phase 1 Evaluation should be performed at least 24 hours after the revascularization procedure but within 30 days post treatment ^b Subjects who are withdrawn prior to the Phase 2 Procedure should also have a Physical Exam at one month post Phase 1 procedure

^c If subject is unable to return to the site for a follow-up visit, they may be contacted by telephone to evaluate the Modified Rankin Scale and Spinal Cord Ischemia Scale

^d For subjects suspected of having a stroke event within 30 days following the index endovascular procedure an additional MRS score should be completed at 90 days following the suspected stroke event but no greater than 120 days post index endovascular procedure.

^eWithin 48 hours of index endovascular procedure

^f CTA of chest/abdomen/pelvis at Screening. CTA of chest at all follow-up visits, except for Dissection Subjects who must have a CTA of chest/abdomen/pelvis at all visits. Imaging Guidelines for CT are located in Protocol. MRA may be used in place of CTA during follow-up if the Subject is contraindicated for CTA.

^g Screening CTA must be ≤90 days prior to Phase 2 procedure.

^h Screening CTA of Head/Neck must be ≤90 days prior to Phase 1 procedure. If CT of Head/Neck is not consistent with site's standard of care then radiological modality of evaluation is at investigator discretion (Ultrasound, MR, etc.) However, imaging of head/neck vasculature is required ≤90 days prior to Phase 1 procedure.

¹NIH Stroke Scale should be performed for all subjects during Screening, Discharge and 1 Month visits. NIHSS should also be performed for any Subject suspected of having a stroke event that undergoes the treating site's stroke Protocol during the study interval from the initiation of the surgical revascularization procedure until discharge post-index endovascular procedure. The scale **GRE** Should be performed as soon as possible after learning of the suspected event.

CONFIDENTIAL INFORMATION

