5.2.2 Zone 0/1 Aneurysm Cohort

The Primary Endpoint for the Zone 0/1 aneurysm cohort will be analyzed after all available Subjects meeting the analysis population criteria have completed the one month follow-up visit and have been in the study through 59 days. Subjects with suspected stroke Primary Endpoint events will need to have been in the study through 120 days before this Primary Endpoint analysis will be performed. This extra time is needed for these Subjects to allow for the Modified Rankin Scale to be assessed at any time during this period.

This analysis will also be repeated with 12 month results (following the same analysis population logic as that outlined for the Zone 2 aneurysm cohort in **Section 5.1.1.1**) with the exception that no hypothesis will be tested.

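### Zone 0/1: a stroke between debranching and the index procedure counts toward the primary endpoint, but Table 2 footnote d orders no 90-day mRS for it

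*SAP*

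**What the plan says.** - **Endpoint period.** SAP 2.3.1.2 counts the Zone 0/1 components, disabling stroke among them, "from the time of enrollment through one month following the index endovascular procedure (through day 59 unless otherwise specified in study protocol component definitions"). The Protocol Summary also starts the period at enrollment.
- **Staging.** The Protocol Summary (Schedule of Events, Zone 0/1) sets "Phase 2 Procedure at least 24 hours but no more than 60 days following the completion of the revascularization procedure". SAP Table 4 places debranching on days -60 to -1, ideally days -7 to -1.
- **Extra mRS.** SAP 4.2, Table 2 footnote d orders it for those "suspected of having a stroke event within 30 days following the index endovascular procedure an additional MRS score should be completed at 90 days" after the event, and no later than day 120. Table 1 footnote b (Zone 2) has the same wording. The Protocol Summary describes the mRS as "also completed at 3 months for Subjects suspected of experiencing a stroke event through 30 days" and names no starting point.
- **NIHSS.** For suspected strokes, the Zone 2 footnote (Table 1, f) runs "from the initiation of the index endovascular procedure until discharge". The Zone 0/1 footnote (Table 2) runs "from the initiation of the surgical revascularization procedure until discharge post-index endovascular procedure".
- **Analysis timing.** SAP 5.2.2 states: "Subjects with suspected stroke Primary Endpoint events will need to have been in the study through 120 days", and gives the reason: "This extra time is needed for these Subjects to allow for the Modified Rankin Scale to be assessed at any time during this period".
- **Adjudication.** SAP Appendix A has disabling stroke reported by the site and then decided by neurologist review within the Clinical Events Committee (CEC).

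**The concern.** The endpoint and the analysis hold cover every suspected stroke endpoint event from enrollment on. The instruction that produces the 90-day score starts only at the index procedure. Within Table 2 the NIHSS trigger was moved back to cover the debranching stage, but the mRS trigger was not. A suspected stroke after debranching that is worked up under the site's stroke protocol therefore gets an NIHSS but no ordered 90-day mRS.

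At stake is whether one component of a tested endpoint is judged on comparable information. Following the schedule as written, a stroke on days 0-30 has a score 90 days after onset. A stroke a few days before the index procedure may have one well before that point and one well after it. The supplied text does not say which score the adjudicators use, so the choice could be made case by case.

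**Working it through.** **The plan's own cut-off.** Inputs: n = 50 and goal 60% (SAP 2.4.3 and the sample-size text that follows it); one-sided exact test at 0.05 (SAP 5.3.1). With X binomial(50, 0.60):
- 37 of 50 (74%): P(X ≥ 37) = 0.0280, lower bound 61.9%; passes.
- 36 of 50 (72%): P(X ≥ 36) = 0.0540, lower bound 59.7%; fails.

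The stated 74% reproduces if read as at least 74%. One subject's classification matters only if the result lands on this boundary.

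**Timing.** Let d be the day of stroke, with the index procedure on day 0. The ideal visit windows in SAP Table 4 are days 23-44 (1 month) and 150-210 (6 months).
- 90-day point = d + 90.
- Days from onset to the 1-month score: 23 - d to 44 - d.
- Days from onset to the 6-month score: 150 - d to 210 - d.

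| Stroke day d | 90-day point (study day) | 1-month score, days after onset | 6-month score, days after onset | Extra mRS ordered by footnote d? |
|---|---|---|---|---|
| -60 | 30 | 83-104 | 210-270 | No |
| -30 | 60 | 53-74 | 180-240 | No |
| -7 | 83 | 30-51 | 157-217 | No |
| -1 | 89 | 24-45 | 151-211 | No |
| 0 | 90 | 23-44 | 150-210 | Yes |
| 30 | 120 | at most 14 | 120-180 | Yes |

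Across the ideal debranching interval, days -7 to -1, the scheduled scores fall at 24-51 and 151-217 days. The 90-day point falls on days 83-89, between the two ideal windows. A Phase 1 score (if that evaluation follows the stroke) and a discharge score may be added. For the earliest possible strokes, near day -60, the 1-month visit already gives a score close to 90 days.

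**Wider windows.** The analysis windows are days 15-59 and 60-242. For d = -7 they allow scores at 22-66 (15 + 7 to 59 + 7) and 67-249 (60 + 7 to 242 + 7) days after onset. For d = -1 they allow 16-60 and 61-243. A score near 90 days is possible, but nothing orders it.

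**Effect of moving the trigger.** For strokes on days -60 to -1 the ordered score would fall on days -60 + 90 = 30 to -1 + 90 = 89, all before day 120.

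**The case against.** **Footnote d and 5.2.2 agree with each other.** A stroke on day 30 has its 90-day score on day 30 + 90 = 120, exactly the hold. This stands. The mismatch is with the start of the endpoint period, not between these two provisions.

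**The definition of disabling stroke is not in the supplied text.** It may name the score to be used, and a neurologist, not a formula, decides. SAP 5.2.2 also accepts an mRS at any time in the hold period. This limits the weight of the point: uneven timing matters only so far as the adjudication relies on a score near 90 days. It does not explain why that score is ordered for strokes after the index procedure and not for those before it.

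**The Protocol Summary gives no starting point for its 30-day limit.** It can be read to include earlier strokes. If that is the intent, footnote d is narrower than the Protocol and still needs correcting.

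**Few subjects are involved.** This stands. Subjects who never start the index procedure already fail on that component. Accrual is expected to take 48-60 months, so most subjects will have a 6-month score before the analysis.

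**A stronger reading is tempting.** A reader might infer that strokes on days 31-59 are missed too and that the hold is too short for them, since 31 + 90 = 121 and 59 + 90 = 149. The documents do not support this as it stands. SAP 2.3.1.2 lets a component definition replace the day-59 limit, and 30 + 90 = 120 suggests a 30-day stroke window.

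**Conclusion.** The point holds for strokes between debranching and the index procedure in subjects who go on to the index procedure. Such a stroke counts, the analysis may be held for its mRS, and no 90-day mRS is ordered. The shared wording with Zone 2, beside an NIHSS footnote that was adapted, suggests a carry-over rather than a choice, though the documents do not say so.

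The size is small. For most affected subjects the problem is when the score is taken; only those enrolled last may lack a later score at analysis. A reader might infer that these strokes go unassessed, or that the test is biased or would change. Neither follows: routine mRS visits remain, the number of such strokes is not given, and the direction of any effect is unknown.

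The conclusion rests on the enrollment start stated in both documents and on footnote d as written. It assumes that the unseen Protocol definition does not itself order a 90-day score for pre-index strokes. It is worth correcting, with medium confidence.

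**What to change.** 1. In SAP Table 2 footnote d, and in the matching Zone 0/1 line of the Protocol schedule, start the trigger at initiation of the surgical revascularization, as the NIHSS footnote does. Keep the mRS at 90 days after the suspected event. SAP 5.2.2 needs no change.
2. For subjects already past that point, state in the SAP that the CEC uses the mRS closest to 90 days after onset, and list these subjects with the timing of the score used.
3. Check the Protocol definition of disabling stroke. Only if it runs to day 59 should the trigger extend to day 59 and the hold to 90 days after the event where that is later (at most day 149).

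**Cost.** One extra mRS for a few subjects; Table 2 footnote c allows a telephone assessment when the subject cannot return. The schedule change needs a Protocol revision and IRB approval at up to 45 sites. If that is judged too much, step 2 alone needs only a SAP change and should be settled before the primary analysis. Sample size, test and pass rule are unchanged.
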